We will be recruiting from various sources in the community for this research study. They include online recruitment sources, community outreach and physician referrals. [name] has years of experience conducting research studies and is well-suited to conduct human research. Our coordinators have experience conducting human research and are very well qualified. All staff members assisting with this trial are adequately informed about the protocol, the investigational products, and their trial-related duties and functions. An anesthesiologist or other appropriately trained physician (e.g., Intensivist) will administer the study drugs to subjects.

The following emergency equipment will be available in setting of study drug administration:

- Defibrillator, suction device, two oxygen cylinders
- Oxygen delivery devices (nasal cannulae)

 Mount Sinai	Protocol Title:	Pharmacologic attenuation of ketamine using nitroprusside
	Principal Investigator Name/Contact Info:	[name]/ [contact]
	Primary Contact Name/Contact Info	[name] / [contact]
	Date Revised:	4/15/2019
	Study Number:	HSM#16-00928/GCO#16-1580

- ECG monitor, pulse oximeter, and an expired carbon dioxide detection device (e.g., EasyCap, etc).
- emergency benzodiazepine reversal, emergency opioid reversal, and resuscitation drugs
- manual resuscitation bag, tracheal intubation equipment
- IV equipment: Angiocath, IV tubing, Saline Bag, IV starter kit
- Saline flush, syringes, needles

Code protocol: A study physician will be available throughout the infusion and during the subsequent monitoring period. In the event that additional medical back up is required, study personnel will call a “Team 7000” to activate the Hospital emergency response team, as well as call 911, which is the standard procedure for emergencies occurring in non-hospital space.

5) Study Design

a) Recruitment Methods

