- 2) Lifetime histories of autism, mental retardation, pervasive developmental disorders, or Tourette’s syndrome;
- 3) Current diagnosis of OCD or eating disorder (bulimia nervosa or anorexia nervosa);
- 4) Subjects with DSM-V drug or alcohol abuse/dependence within the preceding 2 years;
- 5) Patients with schizotypal or antisocial personality disorder, or any clinically significant axis II disorder that would, in the investigator’s judgment, preclude safe study participation;
- 6) Patients judged clinically to be at serious and imminent suicidal or homicidal risk, or suicide attempt within the past 1 year;
- 7) Women who are either pregnant or nursing;
- 8) Any serious, unstable medical illnesses including hepatic, renal impairment, gastroenterologic, respiratory, cardiovascular, endocrinologic, neurologic, immunologic, or hematologic disease;
- 9) History of congestive heart failure, established coronary artery disease, or valvular disease;
- 10) History of cerebrovascular insufficiency;
- 11) History of intrapulmonary arteriovenous shunts, co-arctation of the aorta or other conditions where cardiac outflow tract is obstructed;
- 12) Vitamin B12 deficiency;

Protocol Title:	Pharmacologic attenuation of ketamine using nitroprusside
Principal Investigator Name/Contact Info:	[name]/ [contact]
Primary Contact Name/Contact Info	[name] / [contact]
Date Revised:	4/15/2019
Study Number:	HSM#16-00928/GCO#16-1580

- 13) Clinically significant abnormal findings of laboratory parameters, physical examination, or ECG;
- 14) Renal impairment, as reflected by a BUN > 20 mg/dL and/or creatinin clearance of >1.3 mg/dL;
- 15) Thyroid impairment, as reflected by a TSH > 4.2 mU/L;
- 16) Hepatic injury, as reflected by AST or ALT greater than twice the upper limit of the reference range (AST: >80; ALT >110);
- 17) Patients who have a positive urine toxicology for illicit substances at screening and within 24 hours of the infusion;
- 18) Treatment with an irreversible MAOI within 2 weeks prior to randomization or fluoxetine within 4 weeks prior to randomization;
- 19) Treatment with other antidepressants (classified as SSRIs, SNRIs, Atypical Antidepressants, MAOIs, TCAs) within one week of randomization;
- 20) Previous recreational use of PCP or KET;

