Prior to the infusion VS will be assessed by nursing staff and confirmed by an MD and will need to be stable as per inclusion/exclusion criteria. Patients will be monitored by study nursing staff and by an MD throughout the infusions and for 1 hour of observation after the infusions end. Furthermore, a study anesthesiologist will oversee the study drug infusions. At the end of the observation period a study doctor will evaluate the patient, then the patient will be discharged home accompanied by a responsible adult. Patients will be instructed not to drive for 24 hours following the infusions.

Description of Study Visit Procedures:

Study Visit 0: Screening

Summary of study procedures during this phase:

- *Informed Consent*
- *Structured Psychiatric Interview (SCID)*
- *Physician Evaluation*
- *Medical History*
- *Adverse Events Documentation*
- *Concomitant Medication Documentation*
- *Physical Exam*
- *Vital Signs*
- *Routine Laboratory Tests*
- *Urine Toxicology*
- *Urine Pregnancy Test (if applicable)*
- *EKG*

 Mount Sinai	Protocol Title:	Pharmacologic attenuation of ketamine using nitroprusside
	Principal Investigator Name/Contact Info:	[name]/ [contact]
	Primary Contact Name/Contact Info	[name] / [contact]
	Date Revised:	4/15/2019
	Study Number:	HSM#16-00928/GCO#16-1580

After receiving complete disclosure about the research and opportunity to fully review the consent form, potential participants will be given the opportunity to ask questions. If they choose to take part in the study, then they will be asked to sign the written informed consent form. Psychiatric history will be obtained by a member of the research team using the SCID and the DSM-5 Diagnostic Criteria. A medical history and physical examination will be performed for each patient and basic laboratory tests ordered. This will include: ECG, vital signs (including orthostatic blood pressure measurements), complete blood cell counts, electrolytes, thyroid functioning test, liver function tests, urinalysis, and toxicology screening. A urine pregnancy test will be performed in premenopausal women. Results of these tests will identify patients who should be included or excluded based on criteria stated earlier in this protocol.

Study Visits 1 and 3: Test days

Summary of study procedures during this phase:

- *Vital Signs*
- *Urine Toxicology*
- *Urine Pregnancy Test (if applicable)*
- *Study Drug Infusion 1 and Infusion 2*

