NP should not be used in the setting of compensatory hypertension, where the primary hemodynamic lesion is aortic coarctation or arteriovenous shunting. NP should not be used to produce hypotension during surgery in patients with known inadequate cerebral circulation, or in moribund patients (A.S.A. Class 5E) coming to emergency surgery. Patients with congenital (Leber’s) optic atrophy or with tobacco amblyopia have unusually high cyanide/thiocyanate ratios, and NP should be avoided in these patients. NP should not be used for the treatment of acute congestive heart failure associated with reduced peripheral vascular resistance such as high-output heart failure that may be seen in endotoxic sepsis. Like other vasodilators, NP can cause increases in intracranial pressure. In patients whose intracranial pressure is already elevated, NP should be used only with extreme caution. The hypotensive effect of NP is augmented by that of most other hypotensive drugs, including ganglionic blocking agents, negative inotropic agents, and inhaled anesthetics. Caution should also be exercised in patients with hepatic insufficiency, anemia, hypovolemia, abnormalities of the pulmonary ventilation/perfusion ratio, and high surgical risks. NP has not been tested for effects on fertility.

 Mount Sinai	Protocol Title:	Pharmacologic attenuation of ketamine using nitroprusside
	Principal Investigator Name/Contact Info:	[name]/ [contact]
	Primary Contact Name/Contact Info	[name] / [contact]
	Date Revised:	4/15/2019
	Study Number:	HSM#16-00928/GCO#16-1580

Risks associated with KET

KET is a sedative/analgesic and general anesthetic for human and veterinary use. It may produce mild to moderate increases in blood pressure, heart rate, and cardiac output due to its sympathomimetic effects and can provoke ischemia in patients with underlying coronary artery disease. Overall, however, KET has a favorable acute safety profile. Over the past several decades, KET has been administered as an anesthetic to several million adults and children.

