The reported incidence of KET-induced perceptual disturbances varies from less than 5% to greater than 30% (Knox et al. 1970; White et al. 1980) and may manifest as vivid dreaming, visualization of psychedelic color, suspension in space, kaleidoscopic floating, and out-of-body experiences. Some patients describe these psychic experiences as bizarre or frightening, while others find them pleasurable, joyful, and fascinating. Indeed, KET is also known as “Special K” as a drug of abuse related to PCP. For that reason KET was placed in Schedule III of the Controlled Substance Act in 1999. Nonetheless, when perceptual disturbances occur, they are usually mild and of short duration (Green and Johnson 1990). KET administration has transient effects on symptoms, usually lasting less than 60 minutes and rarely lasting longer than 2 hours (Carpenter 1999). The perceptual disturbances may be more common in those with preexisting psychosis (Lahti et al. 1995).

Several studies have addressed the question of prolonged psychological effects in the general population secondary to its anesthetic use and concluded that KET does not place patients at a greater risk than other anesthetics (Hersack 1994; Reich and Silvay 1989; Schorn and Witwam 1980). There is no evidence in these long-term studies that individuals exposed to KET are at risk of abusing it on follow-up.

Both ourselves and others have safely used KET in a large number of psychophysiological studies in patients with psychiatric disorders as well as in healthy with doses similar to that of the present study. A meta-analysis of a number of these studies found no evidence of behavioral sensitization following repeated KET exposure (Cho et al. 2005).

7) Provisions for Research Related Injury

We have described above the potential risks of the research procedures and the safeguards that will be used to minimize risks. These include termination of research participation if it is believed that such participation endangers a patient's welfare. Monitoring procedures are used to evaluate potential side effects of treatment or of research procedures. The protocol stipulates an extensive medical and psychiatric evaluation of all patients as a condition for research participation.

 Mount Sinai	Protocol Title:	Pharmacologic attenuation of ketamine using nitroprusside
	Principal Investigator Name/Contact Info:	[name]/ [contact]
	Primary Contact Name/Contact Info	[name] / [contact]
	Date Revised:	4/15/2019

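### Exclusion 14 names the wrong creatinine measure, and no exclusion names two conditions in which the protocol says nitroprusside should be avoided

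*Combined protocol and SAP*

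**What the plan says.** Section 5(b) lists 22 numbered exclusions. Number 14 defines renal impairment by two laboratory limits: "Renal impairment, as reflected by a BUN > 20 mg/dL and/or creatinin clearance of >1.3 mg/dL".

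The NP part of section 6, which the protocol says was taken from the package insert, states that patients with congenital (Leber's) "optic atrophy or with tobacco amblyopia have unusually high cyanide/thiocyanate ratios, and NP should be avoided in these patients".

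Three exclusions in section 5(b) might bear on these conditions without naming them:

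- Number 4 concerns "drug or alcohol abuse/dependence within the preceding 2 years".
- Number 8 begins "Any serious, unstable medical illnesses including hepatic, renal impairment" and goes on to list other organ systems, neurologic among them.
- Number 13 reads "Clinically significant abnormal findings of laboratory parameters, physical examination, or ECG".

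Other safeguards are more general:

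- At Visit 0 (section 5(f)), "A medical history and physical examination will be performed for each patient and basic laboratory tests ordered".
- Section 4 says that "An anesthesiologist or other appropriately trained physician (e.g., Intensivist) will administer the study drugs to subjects", and that staff are informed about the investigational products.
- Section 7 makes an extensive evaluation a condition of participation and provides for "termination of research participation if it is believed that such participation endangers" the patient's welfare.
- Section 5(i) lets investigators withdraw a patient over a safety concern.

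**The concern.** Exclusion 14 is an operative numeric threshold that a screener has to apply. As written it cannot be applied to a clearance. Its direction, read literally, would also exclude patients with better renal function, against its own label of renal impairment. A threshold should not have to be reinterpreted by each person who uses it.

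The second gap concerns cyanide, which section 6 treats as one of the two principal hazards of NP. The reason it gives for avoiding NP in the two optic conditions is an unusually high cyanide/thiocyanate ratio. If the exclusion list does not name them, a patient whom the protocol's own safety text says should not receive the drug is not categorically barred from randomization to it.

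What is at stake is eligibility and patient safety. The sample size, the endpoints and the analysis are untouched.

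**Working it through.** The plan states no figure to reproduce. The check is a comparison of texts plus two lines of arithmetic on dose.

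**1. Exclusion 14: which analyte fits?**

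| Feature as written | Creatinine clearance | Serum creatinine |
|---|---|---|
| Unit mg/dL (a concentration) | Does not fit; clearance is volume per unit time | Fits |
| Values above the limit mean impairment | Does not fit; low clearance means impairment | Fits |

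Both features fail for clearance and both fit serum creatinine. The adjacent limit, BUN above 20 mg/dL, has the same unit and direction. One term is wrong.

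**2. NP restrictions in section 6 against the exclusions in section 5(b)**

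| Condition in section 6 | Strength of wording | Related named exclusion |
|---|---|---|
| Aortic coarctation, arteriovenous shunting | Should not be used | No. 11 |
| Inadequate cerebral circulation (surgical setting) | Should not be used | No. 10 |
| Acute congestive heart failure with reduced peripheral resistance | Should not be used | No. 9 (history of congestive heart failure) |
| Moribund patients at emergency surgery | Should not be used | None; cannot arise in this outpatient trial |
| Leber's optic atrophy, tobacco amblyopia | Should be avoided | None |

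Reading exclusions 1 to 22 one by one, 0 of 22 name optic atrophy, amblyopia or tobacco. Conditions that section 6 marks only for caution, such as anemia or raised intracranial pressure, are not counted as gaps.

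**3. Do the general criteria close the gap?**

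- Number 4 does not name tobacco.
- Number 8 requires illness that is serious and unstable. A stable optic neuropathy need not be unstable.
- Number 13 is mandatory once met, but someone must first judge a finding clinically significant, and the condition must show at examination.

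Table 1 and the separate screening protocol are not in the text, so nothing is inferred about which questions or tests are used at screening.

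**4. Exposure of a patient given NP**

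Inputs: 0.5 micrograms/kg/min for 240 minutes (section 5(f)); cyanide outpaces normal disposal above 2 micrograms/kg/min, and the maximum recommended rate is 10 micrograms/kg/min (both section 6).

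- Total dose: 0.5 × 240 = 120 micrograms/kg over 240 / 60 = 4 hours.
- Rate against the cyanide figure: 0.5 / 2 = 25%.
- Rate against the maximum recommended rate: 0.5 / 10 = 5%.

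Section 6 also says that raised cyanide and clinical deterioration have occasionally occurred within a few hours at recommended rates. It does not say how close those rates were to 0.5.

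**The case against.** The strongest reply is that neither item has a demonstrated consequence. Exclusion 14 contains a slip in a phrase that is also misspelled. Label, unit, direction and the neighbouring BUN limit all point to serum creatinine, and no screener could apply a clearance in mg/dL. Renal disease is also covered by the BUN limit and by numbers 8 and 13. That stands: the practical risk is small, and correcting the term is an editorial act.

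On the optic conditions, a physician who knows section 6 has a documented reason to call either one clinically significant and so exclude the patient under number 13. The pre-entry evaluation, the investigators' power to withdraw a patient, and the safety board's power to modify the criteria add further cover. Nothing in the protocol requires every package-insert warning to become a numbered exclusion. The dose is low: section 5(h) calls it the lowest therapeutic dose for hypertension, and only patients randomized to NP/KET at Visit 3 receive NP. These points are fair, and they are why the matter is small.

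They do not remove it. Each safeguard depends on judgement or on recognizing the condition, whereas the protocol gave related named exclusions to the other NP restrictions that could matter here. Among restrictions worded as strongly, the optic conditions are the only ones relevant to this setting without one.

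**Conclusion.** Both parts hold, at minor severity. Exclusion 14 is wrong as written in one term; serum creatinine is almost certainly meant, subject to the investigators' confirmation. The exclusion list names neither Leber's optic atrophy nor tobacco amblyopia, so keeping such a patient off NP is left to clinical judgement. That patient may well be caught, and the claim goes no further than the absence of a categorical bar.

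The documents give no prevalence for either condition, so the expected number of affected patients among the 40 to be randomized cannot be stated. The conclusion rests on the exclusion list in section 5(b) being complete as it appears.

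**What to change.** 1. Reword the creatinine limit in exclusion 14 as serum creatinine above 1.3 mg/dL, keeping the BUN limit, once the investigators confirm the analyte.
2. Add an exclusion for a history of congenital (Leber's) optic atrophy or tobacco amblyopia, checked from the medical history already taken at Visit 0. Keep the warning in section 6.

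The cost is one corrected criterion and one added criterion. No visit, test or patient is added, and the downside is at most a rare extra screen failure.

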	Principal Investigator Name/Contact Info:	[name]/ [contact]
	Primary Contact Name/Contact Info	[name] / [contact]
	Date Revised:	4/15/2019
	Study Number:	HSM#16-00928/GCO#16-1580

Aim III. Evaluate whether the neurobiological mechanisms governing changes in psychiatric states can be inferred through analysis of peripheral biomarkers isolated from blood.

Research Hypotheses

Research Hypothesis I. Patients pre-treated with NP will experience attenuated antidepressant effects (measured by MADRS score) following KET compared to pre-treatment with placebo.

Research Hypothesis II: Patients pre-treated with NP will experience attenuated psychotomimetic effects (e.g., CADSS score) immediately following KET compared to pre-treatment with placebo.

Research Hypothesis III. Changes in peripheral biomarkers profiles will be correlated with changes in mental status (e.g., mood, perception) in depressed patients treated with KET with and without NP pre-treatment.

2) Background

KET has both rapid onset antidepressant (Berman et al. 2000) and psychotomimetic (Krystal et al. 1994) effects in humans. Among the many biochemical properties of this molecule is antagonism at the NMDA receptor (Anis et al. 1983), an ion channel that is highly permeable to calcium. There are a multitude of downstream processes affected by NMDA receptor modulation, one of which is nitric oxide (NO) synthesis (Bredt and Snyder 1989; Sattler et al. 1999). Taken together, these findings for several decades have formed the scientific basis for the hypothesis that the psychotropic properties of KET occur through modulation of NO homeostasis via NMDA activity.

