Subjects undergo a screening period that may last up to four weeks (Visit 0). Eligible subjects then undergo the PLC/KET Test Infusion (Visit 1) and undergo evaluation of treatment response 24 hours following the infusion (Visit 2). For subjects who meet criteria to continue in the study, they are randomized to one of two treatment conditions (PLC/KET or NP/KET) to take place up to four weeks from the Test Infusion (Visit 3). Subjects will again return for evaluation 1 week (+/- 2 days) following Visit 1(Visit 2a). After the second infusion (Visit 3), subjects will return for evaluation at 24 hours (Visit 4) and 1 week (+/- 2 days) following Visit 3 (Visit 5). Subjects will return for a final exit visit (Visit 6) 14 days (+/- 2 days) following the second infusion (Visit 3). Therefore, the total study participation time will be up to 10 weeks.

We anticipate a 2-year project period, during which time approximately 100 patients will be screened, with 40 patients randomized. However, after 8 patients have completed the study, the results will be unblinded to an independent statistician and an interim analysis conducted. On this basis, the study may be terminated, or it may be continued towards the goal of randomizing 40 total patients. A second interim analysis will be conducted once the sample size has doubled, and 16 patients have completed the study. The statistician will receive de-identified coded data only.

e) Study Endpoints

Primary Outcomes

- (a) Change in Montgomery–Asberg Depression Rating Scale (MADRS) compared across PLC/KET and NP/KET administrations.
- (b) Change in four-item positive symptom subscale of the Brief Psychiatric Rating Scale (BPRS), Clinician-Administered Dissociative States Scale (CADSS) and Visual Analog Scale (VAS) scores from Time 0 to Time 40 minutes compared across PLC/KET and NP/KET administrations.

 Mount Sinai	Protocol Title:	Pharmacologic attenuation of ketamine using nitroprusside
	Principal Investigator Name/Contact Info:	[name]/ [contact]
	Primary Contact Name/Contact Info	[name] / [contact]
	Date Revised:	4/15/2019
	Study Number:	HSM#16-00928/GCO#16-1580

Secondary Outcome

Change in molecular profiles obtained from blood draws of subjects at set time points that parallel clinical ratings during infusions of the agents under investigation and post-infusion follow up.

Statistical Analysis

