The **Brief Psychiatric Rating Scale (BPRS)** (Overall and Gorham 1962) is used to assess acute behavioral changes during the infusions. Four key BPRS items for the positive (+) symptoms of psychosis will be used: conceptual disorganization, hallucinatory behavior, suspiciousness, and unusual thought content. Three items representing the negative (-) symptoms of psychosis will also be used: blunted affect, emotional withdrawal, and motor retardation.

The **Clinician-Administered Dissociative States Scale (CADSS)** (Bremner et al. 1998) is used to measure dissociative effects during the infusions. The scale includes 19 questions and 8 observer ratings scored from 0 (not at all) to 4 (extremely). The CADSS measures impairment in body perception, environmental perception, time perception, memory impairment, and feelings of unreality.

Visual Analog Scales. These scales are scored in millimeters from the left-hand side of a 100-mm line to a perpendicular mark made by the patient at a point corresponding to the apparent magnitude of the feeling state. Range: 0 ("not at all") to 100 ("most ever").

Montgomery-Asberg Depression Rating Scale (MADRS) (Montgomery and Asberg 1979). This is a 10-item instrument used for the evaluation of depressive symptoms in adults and for the assessment of any changes to those symptoms. Each of the 10 items is rated on a scale of 0 to 6, with differing descriptors for each item. These individual item scores are added together to form a total score, which can range between 0 and 60 points. The estimated time to administer this scale is 20 minutes. Inter-rater reliability of the scale is high and scores correlate significantly with those of the HAM-D. On the infusion days a modified MADRS will be used that will exclude the sleep and appetite items.

Quick Inventory of Depressive Symptomatology, Self Report (QIDS-SR): The Quick Inventory of Depressive Symptomatology, Self Report (QIDS-SR) is a 16-item self rated instrument designed to assess the severity of depressive symptoms. The 16 items cover the nine symptom domains of major depression as indicated by the DSM, and are rated on a scale of 0-3. Total scores range from 0 to 27, with ranges of 0-5 (normal), 6-10 (mild), 11-15 (moderate), 16-20 (moderate to severe), and 21+ (severe).

Columbia-Suicide Severity Rating Scale (C-SSRS): The Columbia-Suicide Severity Rating Scale (C-SSRS) is a comprehensive, semi-

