2. Justify your choice of principal monitor in terms of the assessed risk to the research subject's health and wellbeing. In high risk studies when the principal monitor is independent of the study staff, indicate the individual's credentials, relationship to the PI, and the rationale for selection.

[name] is intimately knowledgeable of this study and also be involved in the clinical care of the subjects and will provide oversight of

 Mount Sinai	Protocol Title:	Pharmacologic attenuation of ketamine using nitroprusside
	Principal Investigator Name/Contact Info:	[name]/ [contact]
	Primary Contact Name/Contact Info	[name] / [contact]
	Date Revised:	4/15/2019
	Study Number:	HSM#16-00928/GCO#16-1580

the entire study. He has been involved in many KET studies in Mood and Anxiety Program (MAP).

3. List the specific items that will be monitored for safety (e.g., adverse events, subject compliance with the protocol, drop outs, etc.).

Adverse events, subject compliance with the protocol, side effects and dropouts will be closely monitored.

4. Indicate the frequency at which ACCUMULATED safety and data information (items listed in number 3 above and interim analysis of efficacy outcomes) will be reviewed by the monitor(s) or the Data Monitoring Committee (DMC). Although this information must be reviewed at least annually, the higher the study risks, the more frequently reviews must be scheduled.

All accumulated data will be reviewed annually by the PI and the IRB. In addition, data and safety will be monitored in an ongoing fashion by the PI.

5. Where applicable, describe rules which will guide interruption or alteration of the study design.

N/A

6. Where applicable, indicate dose selection procedures that will be used to minimize toxicity.

The dose of KET is fixed with 0.5 milligrams/kg/hour infusion over 40 min. NP is administered at the lowest therapeutic dose used for treatment of hypertension, 0.5micrograms/kg/min. The time of 240 minutes for the infusion was determined through the only published study of the use of NP as a psychotropic medication in humans (Hallak, 2013).

7. List any specialized grading system that will be used to evaluate adverse events (e.g., National Cancer Institute Common Toxicity Criteria).

Grading of severity and attribution to research will be conducted at each visit and noted on the treating cover sheet.

(1) Attribution of adverse events:

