The DSMB will ensure the safety of study participants and the integrity of the data collection in the projects. To achieve this goal, the DSMB will perform an ongoing evaluation of the safety of patients participating in the clinical outcomes in the clinical trial. This includes monitoring adverse events and overall clinical outcomes in the studies. Through this process the board will evaluate the need for study termination and/or modification of study criteria for inclusion, exclusion, or discontinuation. In

Protocol Title:	Pharmacologic attenuation of ketamine using nitroprusside
Principal Investigator Name/Contact Info:	[name]/ [contact]
Primary Contact Name/Contact Info	[name] / [contact]
Date Revised:	4/15/2019
Study Number:	HSM#16-00928/GCO#16-1580

addition, the DSMB will be responsible for the evaluation of the adherence to written protocols regarding the protection of human subjects and the assurance of identity protection as specified in the Data Sharing Section. The DSMB will expeditiously review all serious adverse events and perform ongoing scheduled reviews of non-serious adverse events and study dropouts. The DSMB includes the following members: The Oversight Committee members are to include: [name], Professor of Psychiatry, Brown University; [name], Icahn School of Medicine Professor of Anesthesiology; [name], Professor of Psychiatry, Icahn School of Medicine at Mount Sinai; and [name], Professor of Neurology and Professor of Anesthesiology, Icahn School of Medicine at Mount Sinai. The board will review the project's data and safety on bi-annual basis and report their findings to the PI.

i) Withdrawal of Subjects

Investigators may elect to withdraw the patient due to safety concern or non-adherence to the study protocol. Subjects may withdraw at any point in the study.

6) Risks to Subjects

Risks associated with NP [The following information was derived from the FDA package insert for NP (Nitropress [package insert]. Lake Forest, IL: Hospira Inc; 2014).]

The principal hazards of NP excessive hypotension and excessive accumulation of cyanide. Transient excesses in the infusion rate of NP can result in excessive hypotension, sometimes to levels so low as to compromise the

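### Unblinded looks at 8 and 16 completers have no stated purpose, endpoint or boundary; three primary Aim II scales have no success rule; and the Aim II rating window, read literally, closes before ketamine starts

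*Combined protocol and SAP*

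**What the plan says.** **Looks.** Section 5(d) unblinds results to an independent statistician after 8 completers and continues: "On this basis, the study may be terminated, or it may be continued towards the goal of randomizing 40 total patients". It then says: "A second interim analysis will be conducted once the sample size has doubled, and 16 patients have completed the study". No consequence is attached to the second look.

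**Monitoring.** Section 5(h) Part I item 5 asks the sponsor to "describe rules which will guide interruption or alteration of the study design"; the answer is N/A. Item 4 asks how often accumulated data, expressly including interim efficacy analyses, will be reviewed. The answer is "All accumulated data will be reviewed annually by the PI and the IRB", plus ongoing monitoring by the PI; neither look is mentioned. Part II sets up a DSMB that meets bi-annually and reports to the PI. Of its remit it says: "Through this process the board will evaluate the need for study termination and/or modification of study criteria for inclusion, exclusion, or discontinuation".

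**Aim II endpoints.** Section 5(e), Primary Outcomes (b), lists the four-item BPRS positive subscale together with "Clinician-Administered Dissociative States Scale (CADSS) and Visual Analog Scale (VAS) scores from Time 0 to Time 40 minutes". The Statistical Analysis text states a single null (b) for psychotic rating scores as a group. It plans an overall F test followed by post-hoc t-tests, with no rule across scales. Section 5(f), Description of Study Instruments, describes VAS in the plural ("These scales are scored in millimeters from the left-hand side of a 100-mm line") without giving a number. Research Hypothesis II in section 1 gives one scale as its example: "Patients pre-treated with NP will experience attenuated psychotomimetic effects (e.g., CADSS score) immediately following KET".

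**Aim I endpoint.** Primary Outcomes (a) is change in MADRS with no time point. Section 5(d) schedules evaluations at 24 hours, 1 week and 14 days after the second infusion.

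**Clock.** In section 5(f), Description of Study Drug Procedures, Time 0 is the start of Infusion 1 (nitroprusside or placebo), ketamine starts at 200 minutes and both end at 240. Section 19 also puts ketamine 200 minutes after Infusion 1.

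**The concern.** The plan lets unblinded results influence whether the trial continues, but does not say what is tested, against what threshold, or who acts. A rule written after the data are seen cannot be shown to be independent of them. An analyst who follows section 5(e) also cannot tell whether success on one Aim II scale is success for the aim. Two analysts could read the same data and report opposite conclusions, both within the plan.

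The clock conflict bears on validity rather than error rate. A window that closes before ketamine is given cannot measure symptoms caused by ketamine.

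**Working it through.** **Inputs.** From the documents: 40 randomized, looks at 8 and 16 completers, three named Aim II scales. Not in the documents, so assumed: 1:1 allocation, one between-arm t-test on change per scale, equal correlation rho between scales, and alpha of 0.05 two-sided or 0.025 one-sided.

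**The plan's own figure.** The target of 40 cannot be reproduced, because no alpha, power, effect or SD is given. Solved backwards, 20 per arm at two-sided 0.05 and 80% power detects 0.91 SD.

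**1. Any one of three scales suffices, no looks.** At rho = 0 the risk is 1 − (1 − α)³:
- two-sided 0.05: 1 − 0.95³ = 14.3%
- one-sided 0.025: 1 − 0.975³ = 7.3%

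For rho > 0, from the equicorrelated normal distribution:

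| rho | two-sided 0.05 | one-sided 0.025 |
|---|---|---|
| 0 | 14.3% | 7.3% |
| 0.5 | 12.5% | 6.3% |
| 0.7 | 10.9% | 5.5% |
| 0.9 | 8.4% | 4.2% |

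In either column the risk is 2.9 times the nominal level at rho = 0 and 1.7 times at rho = 0.9. There is no floor at 8.4%: at rho = 0.95 the two-sided figure is 7.3%, and it tends to 5% as rho tends to 1. If VAS is two scales (four tests), the two-sided range is 18.5% to 9.4% for rho 0 to 0.9.

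**2. All three scales required.** The risk cannot exceed that of any single test, so it is at most 5% at 0.05 per scale.

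**3. Only if each look is also an unadjusted two-sided 0.05 efficacy test.** Simulated t-tests at 4, 8 and 20 per arm give about 12% for one scale. For any of three scales they give 32%, 29%, 25% and 20% at rho 0, 0.5, 0.7 and 0.9.

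**4. Looks for futility or safety only.** They add no false positives; the figures in steps 1 and 2 apply.

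**5. Size of an effect that stops the trial at 8 completers.** With 4 per arm, p < 0.05 needs an observed difference of t(0.975; 6 df) × √(2/4) = 2.447 × 0.707 = 1.73 sample SD. Significant results in the true direction average:

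| True effect (SD) | Power | Mean estimate (true SD) | Ratio |
|---|---|---|---|
| 0.5 | 9% | 1.59 | 3.2 |
| 0.8 | 16% | 1.71 | 2.1 |
| 0.91 | 19% | 1.75 | 1.9 |

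**6. Clock.** On the section 5(f) clock the Aim II window ends at 40 minutes and ketamine starts at 200. The window therefore closes 200 − 40 = 160 minutes before ketamine begins.

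**The case against.** **The looks may not be efficacy looks.** A reader might infer that the plan permits an early positive claim and that 20% to 32% is the trial's error rate. The documents do not support that. They allow termination without saying for what, and futility or safety looks would leave the error rate unchanged. What stands is that the plan does not say which.

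**There is oversight.** It would be wrong to infer that nobody can stop the trial. The DSMB covers safety and overall clinical outcomes and has a general remit on termination, and the PI and IRB review accumulated data. What stands is narrower: section 5(d) sends the results of these two looks to none of them.

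**The three scales may be meant jointly.** Section 5(e) joins them with an and, under one null, so the all-required reading is open, and on it the risk is at most 5%. Null (b) is also directional, so one-sided 0.025 is a fair reading. Both points limit the size of the problem. Neither supplies the missing rule.

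**The planned model was not simulated.** The plan treats Treatment Condition as a within-subject factor; the figures here are between-arm. Step 1 carries over only if each scale's test holds its own level. The figures at 8 completers assume an exact 4/4 split. No ratio or blocking is stated, and simple 1:1 randomization gives that split with probability 70/256 = 27%.

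**The window may be timed from the start of ketamine.** Ketamine runs for 40 minutes, so this is plausible, but section 5(e) does not say so and section 5(f) defines Time 0 otherwise.

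**Conclusion.** The gaps are real and should be closed. Neither look has a stated purpose, endpoint or boundary, and no body is assigned to act on it. Three primary scales share one null with no success rule. The Aim II window contradicts the infusion clock. The Aim I endpoint has no time point.

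The numerical consequence is conditional. With no looks and any one scale sufficing, the risk is 14.3% to 8.4% at two-sided 0.05 and 7.3% to 4.2% at one-sided 0.025, for correlation 0 to 0.9. It is higher if VAS is several scales, and at most 5% if all three are required. Only unadjusted two-sided 0.05 efficacy testing at the looks would raise it to about 12% per scale and 32% to 20% for any of three. If an efficacy stop at 4 per arm were allowed, it would overstate the effect about two- to threefold. These are scenarios under the stated assumptions, not properties of the plan.

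The documents do not say whether the look at 8 has already taken place, so no conclusion can be drawn about decisions already made.

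**What to change.** All changes are to wording; none needs new patients or data.

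1. **Section 5(e), Aim II.** Name one primary scale (CADSS is the example in Research Hypothesis II), or apply Holm across BPRS positive, CADSS and one specified VAS score. State alpha and sidedness. One named scale costs no alpha. Holm's strictest step (0.05/3 = 0.0167) moves the effect detectable with 80% power at 20 per arm from 0.91 to 1.06 SD.

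2. **Sections 5(d) and 5(h) item 5, before any further unblinded look.** Choose one:
   - Neither look permits an efficacy claim, and the final test stays at 0.05. This costs nothing.
   - An efficacy claim at a look needs p < 0.001 on that aim's named endpoint, with the final test at 0.0485. Simulated overall error is then 0.0499, against 0.0514 if the final test stays at 0.05. The detectable effect moves from 0.909 to 0.914 SD. An early claim would be rare: it needs an observed 4.21 sample SD at 4 per arm or 2.07 at 8 per arm. If Holm is used, name one scale as the trigger.

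   In either case, state what each look can lead to, who decides, and that the results go to the existing DSMB. Any futility criterion is the sponsor's choice. One example is a non-binding stop at 16 if neither aim's named endpoint differs in the hypothesised direction. It would stop 25% to 33% of trials with no effect on either aim. With a true 0.91 SD effect on one aim only, it would cost less than one percentage point of power.

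3. **Sections 5(e), 5(f) and 19.** Reconcile the Aim II rating window with the infusion clock and state the zero point for the ratings.

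4. **Section 5(e), Aim I.** Name one MADRS time point; 24 hours would match the response criterion already used at Visit 2.
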